The stimulation unit for the extended electronic muscle stimulation (vest with stimulation module for the legs) (courtesy of MihaBodytech Augsburg)

FIGURE 3

Demonstration of potential physical exercises that can be undertaken while applying whole body electronic muscle stimulation using the MihaBodyTec (Gersthofen, Germany) device

FIGURE 4

Guideline for Safe and Effective WB-EMS

In General

1. Safe and effective Whole-Body-EMS Training must be advised and accompanied by a trained and licensed WB-EMS trainer or scientifically trained personnel familiar with this field of application.
2. Before the first training session of every beginner, an anamnesis of possible contraindications based on a list of questions must be taken and then documented in writing, confirmed by the client's signature and archived. Where relevant anomalies are found, a doctor is to be consulted and training only be commenced if clearance has been given.

Preparing for Training

1. As with any kind of intensive training, Whole-Body EMS training must only be carried out in a good physical condition and free of pain. This includes abstaining from alcohol, drugs, stimulants/muscle relaxants or stress ahead of the training session. Training must never be carried out by anybody suffering from an illness with fever.
2. Whole-Body-EMS training leads to very high metabolic stress of the organism because of very high volume of muscle mass addressed. This factor has to be taken into account through sufficient food intake that is as high in carbohydrates as possible. If this is not possible, then at least a high carbohydrate, but light snack (~250kcal) should be eaten, ideally about 2 hours before training.
3. So as to avoid possible renal stress (especially with undiagnosed problems) through intensive WB-EMS, additional fluids should be consumed before/during and after training (500ml each).
4. Generally, medical – ideally sport-medicinal – consultation and clarification is advisable in the case of any discomfort, physical restrictions, infections or other internal, cardiological or orthopedic illnesses.

Training

1. Regardless of physical status, sport experience and the user's wishes to that effect, under no circumstances may WB-EMS training to exhaustion take place during the first training session or trial training. In the past, this has led to undesired side effects and negative health consequences and must be avoided at all costs.

2. After moderate initial WB-EMS, the stimulation level or current must be successively increased and adapted to the individual goals. The highest level is to be reached only after 8-10 weeks of systematic training at the earliest (user's subjective effort impression: hard-hard+). Training to complete exhaustion, especially in the sense of painful, continuous tetanus during the current phase, must generally be avoided.
3. In addition, the initial training should be conducted with a reduced effective training period. Advisable is 5min impulse familiarization and a curtailed training session with moderate stimulus intensity (user's subjective effort impression: a bit hard) and 12min intermittent load with short impulse phase (~4s). Only then should the training duration be cautiously increased and never exceed 20min.
4. To ensure sufficient conditioning and to minimize or rule out possible health impairments, training frequency may not exceed one training unit per week during the first 8-10 weeks.
5. Even after this conditioning phase, an interval of ≥ 4 days must be maintained between training units in order to avoid accumulation of muscle breakdown products, permit regeneration and adaptation and thus ensure a successful training outcome.

Safety Aspects During and After Training

1. During the training session, the trainer or the trained and qualified personnel should concentrate exclusively on the interests of the user(s). Before, during and after training the trainer verbally and visually checks the user's condition so as to rule out health risks and ensure effective training. Training is to be stopped immediately if there are any contraindications.
2. During training, the equipment's operating controls must be directly in reach of the trainer and the user at all times. Operation/adjustment must be simple, quick and precise.
3. Actually, we generally advise against private use of technology without support of a qualified and licensed trainer/instructor or correspondingly scientifically trained personnel.

Safety recommendations put forward by a German consensus conference in December 2015, consisting of whole body-EMS manufacturers (miha-bodytec, Gersthofen, Germany), educational institutions (GluckerKolleg, Kornwestheim, Germany), Licensees (PT Lounge Koln, Cologne, Germany) and publishing researchers. In April 2016, the scientific part of the consortium (Frohlich, M.; Kemmler, W.; Kleinoder, H. v. Stengel, S.) formulated these general safety guidelines

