- vi) A significant improvement in symptoms of angina as measured by the Rose Questionnaire
- vii) A significant improvement in quality of life as measured by the LASA Questionnaire, symptoms of depression as measured by the PHQ-9 Questionnaire, and symptoms of stress as measured on the Perceived Stress Scale
- viii) No significant difference in blood levels of creatinine kinase across time
- viii) A significant improvement in sensorimotor characteristics (visual-motor reaction time, peak knee muscular force, muscular force steadiness, standing balance, and overhead squatting posture)
- ix)

Methods

Trial Design

This study will consist of a **blinded randomized controlled prospective study design**, and will include 80 healthy individuals who are employees at Mayo Clinic, Rochester MN.

Excluded subjects will consist of:

- Subjects under the age of 18
- Pregnancy/or suspected pregnancy
- Subjects with a history of liver or kidney disease, acute illness, taking medications (such as glucocorticoids)
- Subjects who have conditions (such as chronic inflammatory muscular diseases or Cushing's syndrome) that affect muscle mass

- Individuals with pacemakers and implantable cardiac defibrillators
- Individuals who conduct any other type of resistance training (> 45 minutes/week)
- Individuals who have regular “high” alcohol consumption (> 80g/day on 5 days a week), or are under acute influence of alcohol, drugs narcotics, and/or painkillers
- Subjects unable to consent to or participate in the 16-week EMS intervention or be available for follow up (1).
- Subjects who report recent surgeries
- Cardiac arrhythmias
- Active medical implants
- Epilepsy
- Seizures
- Severe circulatory disorders
- Arterial circulatory disorders
- Strong bleeding tendencies (hemophilia)
- Bleeding
- Abdominal wall hernia
- Inguinal hernia
- Tuberculosis
- Tumor diseases
- Arteriosclerosis in advanced stage
- Severe neurological disorders
- Diabetes mellitus
- Febrile diseases
- Acute bacterial or viral infections
- Liver diseases
- Kidney diseases
- Cardiovascular diseases
- Coronary heart diseases
- Infected or wounded areas of the skin
- Skin cancer
- Rhabdomyolysis

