and guided by two certified instructor (i.e., two applicants coached by one instructor). Whole body-EMS will be conducted on approximately the same day, once a week (i.e., $1.0 \times \text{week}$) for 20 minutes. The device will apply a bipolar electric current; we will select an impulse frequency of 85 Hz, an impulse width of 350 μs , and will apply an interval approach with 4 seconds of stimulation alternating with 4 seconds of rest. Gentle slight dynamic exercises will be performed during the 4-second stimulation phase. Each session will consist of 10–14 dynamic exercises structured in one to two sets of eight repetitions performed without any additional weights in a standing position. Most exercises will be based on a low amplitude squat exercise ($< 35^\circ$ leg flexion) with full amplitude movements of the arms (such as rowing, lat pulley, or butterfly). The emphasis of the protocol however will not be the effect on muscles induced by voluntary activation but by the application of whole body-EMS with high current intensity during functional movements. During the course of the study, the instructor will progressively increase the volume of stimulation by extending the length of the session from 14 up to 20 minutes after 4 weeks of training. The intensity of the stimulation will be regulated using a rate of perceived exertion (RPE) scale to generate a sufficient, but tolerable, intensity of EMS application to all stimulated areas. For each of the muscle groups stimulated, participants will be encouraged to exercise at a RPE of “6–7 out of 10” (i.e., “hard+ to very hard”) on the Borg CR10 Scale (5). This specification will be achieved in close interaction between the participant and instructor. Based on initial start settings determined after 4, 8, and 12 weeks, the impulse intensity will be increased slightly every 3 minutes to maintain/slightly increase the prescribed RPE during each session (**refer to Supplemental Video**).

Schedule of events

| | Baseline Day 0 | Weeks 1-7 | Week 8 follow-up (+/- 7 days) | Weeks 9-15 | Week 16 follow-up (+/-7 days) |
|---|----------------|-----------|-------------------------------|------------|-------------------------------|
| Informed Consent | X | | | | |
| Brief review of medical history | X | | | | |
| Exercise with EMS device | X | X | X | X | X |
| Blood draw and laboratory testing** | X | | | | X |
| Creatinine Kinase | X | | X | | X |
| Physical Assessment* | X | | | | X |

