Previous studies have demonstrated dependence of the RH-PAT score on nitric oxide, confirming that reported RH-PAT scores indeed reflect changes in nitric oxide– dependent endothelial function, rather than neurohormonal activation (15). The reactive hyperemia protocol will consist of a 16-minute reactive hyperemia test, in the following sequence. A five-minute baseline measurement, after which a blood pressure cuff on the test arm will be inflated to 60 mmHg above baseline systolic blood pressure, or at least 200 mmHg for five minutes (occlusion of pulsatile arterial flow will be confirmed by the reduction of the PAT tracing to zero) after which, the cuff will be deflated, and the post-deflation PAT tracing will be recorded for an additional six minutes. The ratio of the PAT signal after cuff release compared to baseline will be calculated through a computer algorithm automatically normalizing for baseline signal, and indexed to the contralateral arm. The calculated ratio reflects the RH-PAT score (scores below 1.7 will be considered consistent with abnormal peripheral endothelial function).

Although RH-PAT scores may not be the gold standard for endothelial function, several studies have shown good correlation between these methods and more widely accepted methods of

endothelial function testing, such as intra-arterial acetylcholine infusion and brachial artery Doppler ultrasound following reactive hyperemia (11, 13, 14).

Laboratory Testing: Laboratory testing will be undertaken in all participants at baseline, and at 16-weeks follow-up in both the intervention and control group. Venous blood will be drawn for high-sensitivity CRP, uric acid, fasting glucose, HbA1c, lipid panel, lipoprotein A, homocysteine and fibrinogen. For patients in both groups, venous blood will also be tested for creatinine kinase levels at baseline, 8-weeks (halfway into the training programs), and 16-weeks (after completing each respective training program for both groups). A blood sample of approximately 30 mL will be drawn and all samples will be sent to the Mayo Clinic central laboratory for analysis.

Body Weight, Height, and Waist Circumference: Body height, weight and waist circumference will be measured using calibrated devices. Body mass index will be calculated as mass (kg)/height (m²).

VO2 MAX and Maximal Heart Rate: This will be tested using exercise treadmill testing in the conventional manner.

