An important issue that has arisen with EMS training is the potential risk of elevation in blood creatinine kinase levels. Studies investigating the effects of EMS on creatinine kinase levels have shown that the electrical stimulus from EMS can cause significantly more stress to the muscular system and therefore could lead to higher creatinine kinase levels compared to voluntary muscle contraction exercise (88, 91). Indeed, due to the ability to innervate large muscle areas simultaneously with dedicated individual intensity to each muscle group, EMS can be associated with potential muscle injury. One study showed that, compared to traditional strength training, the stress on the muscular system is about 40% higher after intensive EMS (88). The authors arrived at the conclusion that the level of stimulation intensity is responsible for the elevation in creatinine kinase, while the duration of stimulation had no influence. The authors also showed that subjects still exhibited high values after long periods ranging from 24 hours to 4 days. Further stimulation within this time of decomposition would result in a cumulative rise in creatinine kinase levels (88), which in turn could overstress the muscular system further. Further, one study in which whole body EMS was implemented to the point of exhaustion in healthy novices confirmed very high elevations in creatinine-kinase levels. Although this study did not detect any of the reported clinical consequences of this “severe” rhabdomyolysis, in less fit subjects who are neither optimally prepared nor supervised, initial whole body EMS to exertion may have more far-reaching consequences. Consequently, EMS requires a greater interval between training sessions to prevent overstressing the muscular system and to ensure strength adaptations compared to conventional training. Of note, a subsequent whole body EMS conditioning phase of 10 weeks completed by a second EMS test application to exhaustion demonstrated creatinine-kinase peaks in the range of conventional resistance exercise

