3. So as to avoid possible renal stress (especially with undiagnosed problems) through intensive WB-EMS, additional fluids should be consumed before/during and after training (500 ml each).
4. Generally, medical – ideally sport-medicinal – consultation and clarification is advisable in the case of any discomfort, physical restrictions, infections or other internal, cardiological or orthopedic illnesses.

Training:

1. Regardless of physical status, sport experience and the user's wishes to that effect, under no circumstances may WB-EMS training to exhaustion take place during the first training session or trial training. This has led in the past to undesired side effects and negative health consequences and so must be avoided at all costs.
2. After moderate initial WB-EMS, the stimulation level or current must be successively increased and adapted to the individual goals. The highest level is to be reached only after 8-10 weeks of systematic training at the earliest (user's subjective effort impression: hard-hard+). Training to complete exhaustion, especially in the sense of painful, continuous tetanus during the current phase, must generally be avoided.
3. In addition, the initial training should be conducted with a reduced effective training period. Advisable is 5 min impulse familiarization and a curtailed training session with moderate stimulus intensity (user's subjective effort impression: a bit hard) and 12 min intermittent load with short impulse phase (\square). Only then should the training duration be cautiously increased and never exceed 20 minutes.

4. To ensure sufficient conditioning and to minimize or rule out possible health impairments, training frequency may not exceed one training unit per week during the first 8-10 weeks.
5. Even after this conditioning phase, an interval of ≥ 4 days must be maintained between training units in order to avoid accumulation of muscle breakdown products, permit regeneration and adaptation and thus ensure a successful training outcome.

Safety aspects during and after training

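### The protocol reproduces a warning about renal stress from intensive WB-EMS, but it has no entry check that would find an undiagnosed kidney problem and no assay that would show renal change

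*Combined protocol and SAP*

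**What the plan says.** **The hazard.** Item 3 of the preparation advice appears both in the section Guidelines for safe and effective WB-EMS and in Figure 4. It begins "So as to avoid possible renal stress (especially with undiagnosed problems) through intensive WB-EMS" and goes on to recommend extra fluids around each session. Efficacy and Safety Considerations describes a study of healthy novices that "confirmed very high elevations in creatinine-kinase levels" after whole-body EMS taken to exhaustion. It adds that the study found none of the clinical consequences reported for rhabdomyolysis.

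**The exclusion.** Methods, Trial Design excludes "Subjects with a history of liver or kidney disease, acute illness" and lists kidney diseases again as a separate item. It gives no test and no method of ascertainment.

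**Entry checks.** The Schedule of events lists "Brief review of medical history" at Day 0. The reproduced guideline adds a signed, question-based check for contraindications, with a doctor consulted if something relevant is found. Trial Design mentions chart review only for cardiovascular risk factors.

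**Laboratory tests.** Outcomes and Measurements, Laboratory Testing states: "Venous blood will be drawn for high-sensitivity CRP, uric acid, fasting glucose, HbA1c, lipid panel, lipoprotein A, homocysteine and fibrinogen". These are run at baseline and week 16. CK, which the protocol spells creatinine kinase, is run at baseline, week 8 and week 16. The only urine test is for pregnancy.

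**The concern.** The protocol repeats a warning that singles out people whose kidney problem is not yet known. The checks it describes at entry depend on what the participant or the record already knows, so they cannot identify that group. The measurements taken afterwards do not include the organ named in the warning.

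Two things are at stake. The first is participant safety, because the stated exclusion does not reach the people about whom the warning is most specific. The second is what the trial can report. It hypothesises no significant difference in CK over time, so it will say something about muscle. With no renal measurement it will have no laboratory evidence about the kidney in either arm, and a reader could take an unremarkable CK result as broader reassurance than it gives.

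**Working it through.** The plan states no figure on this point, so there is nothing to reproduce. The check compares sections and then gives a sense of scale.

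**Step 1. Is the hazard only in a figure?** No. The same item stands in the body text and in Figure 4.

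**Step 2. Is the guideline's precaution carried into the study procedures?** The Intervention section specifies frequency, session length, current settings, exercises, supervision and target exertion. It does not mention fluids.

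**Step 3. Can the entry checks find an undiagnosed problem?** A history review and a list of questions record what is already known. Chart review is not stated for renal status. No test precedes enrolment except the pregnancy test.

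**Step 4. Does any assay measure renal function?**

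- The listed assays are hs-CRP, uric acid, fasting glucose, HbA1c, lipid panel, lipoprotein A, homocysteine and fibrinogen: eight in all, plus CK.
- Serum creatinine, estimated GFR, urea, cystatin C and urinalysis do not appear in the Schedule of events, Laboratory Testing or Statistical Analysis.
- Uric acid is listed under inflammatory markers and homocysteine under novel cardiovascular markers. Neither is planned as a renal test.
- CK is a muscle enzyme. The protocol's spelling should not be read as a creatinine measurement.

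The number of renal function tests planned is 0 at baseline, 0 at week 8 and 0 at week 16.

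**Step 5. Scale, by assumption only.** Inputs from the documents are 80 participants and 1:1 allocation, hence 80 / 2 = 40 in the EMS arm. The share p with an undiagnosed renal problem is not in the documents, so a range of 0.5% to 5% is assumed. The expected number among all 80 is 80p. The chance of at least one in the EMS arm is 1 − (1 − p)^40.

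| p (assumed) | 80p | 1 − (1 − p)^40 |
|---|---|---|
| 0.5% | 0.4 | 1 − 0.995^40 = 18% |
| 1% | 0.8 | 1 − 0.99^40 = 33% |
| 2% | 1.6 | 1 − 0.98^40 = 55% |
| 5% | 4.0 | 1 − 0.95^40 = 87% |

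**Step 6. Assay load.** One added assay at each of the three CK draws gives 80 × 3 = 240 at most.

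**The case against.** The strongest reply is that the guideline does not ask for a renal test. Its sentence goes on to recommend fluids for everyone, and it does not bar people with undiagnosed problems. A reader might infer that the plan breaks its own guideline by omitting a test, and the documents do not support that. The gap between sections is narrower: the fluids are not written into the Intervention section.

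Other parts of the reply also stand:

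- The very high CK values came from EMS to exhaustion in novices and without clinical consequences. This trial is supervised and regulates intensity by perceived exertion. Even so, the Intervention section describes high current intensity and a target of hard+ to very hard, while the guideline describes its highest level as hard to hard+, reached after 8 to 10 weeks at the earliest. Those passages need reconciling, and they make it difficult to set the warning aside as not applying here.
- The Schedule of events puts the baseline draw and EMS exercise both on Day 0. A baseline result can inform eligibility only if it is available before the first session, and the documents do not show that it would be.
- Efficacy and Safety Considerations says that muscle adapts in as little as 3 weeks and that raised CK persists for 24 hours to 4 days. No draw falls in weeks 1 to 7, so three draws could miss a transient early change. Creatinine also partly reflects muscle mass.

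These points limit what an added assay can deliver, but they do not close the gap. Fluids are not a stated study procedure and would not show whether harm occurred. Neither trainer checks nor CK measure renal function.

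**Conclusion.** The point holds in a limited form. The protocol names renal stress as a hazard, applies its kidney exclusion without any test, and measures no renal function at any visit. An undiagnosed problem would not be screened out, and laboratory or subclinical renal change would go unseen. This is a worthwhile low-cost improvement and does not affect the primary EndoPAT analysis.

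Three stronger readings should be avoided:

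- **That people with undiagnosed kidney problems are in fact enrolled.** This depends on a prevalence the documents do not give. The 18% to 87% range rests entirely on the assumed 0.5% to 5% and on 40 people in the EMS arm.
- **That renal harm could not be seen at all.** The guideline has the trainer check each user verbally and visually before, during and after training, so symptomatic harm could surface.
- **That adding the assay would let the trial put an upper limit on renal risk if nothing were found.** No renal event is defined, so there is nothing to count.

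**What to change.** 1. Add a routine renal function measure, for example serum creatinine with estimated GFR, to the blood already drawn for CK at baseline, week 8 and week 16. List it in the Schedule of events, Laboratory Testing and Statistical Analysis.
2. Make the baseline result available to the investigator before the first EMS session, and state in Trial Design how the kidney-disease exclusion is ascertained.
3. Report values and changes by arm, beside CK.
4. Reconcile the guideline section and Figure 4 with Trial Design and the Intervention section, including whether the guideline's fluid advice is a study procedure.

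The choice of test, any threshold and any action on a result are for the investigators.

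**Cost.** At most 240 assays, possible rescheduling of the Day 0 draw or of the first session, and perhaps a few more screen failures. The measure will not reliably catch transient early change, and the report should say so.
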